7.5.4 Device Removal

If at the time of a scheduled dosing it is not possible to administer a full medication dosage as per the standard administration steps detailed in the device's IFU due to a device related issue, the IDDD will be declared a device malfunction. If the device malfunction is irreversible and cannot be corrected without a device surgical intervention, the IDDD will be declared a device failure, starting from the date of the initial malfunction.

The IDDD will then be surgically removed or revised and a new device and/or device components will be re-implanted at the earliest possible opportunity, preferably at the same time.

Details of the device removal will be recorded in the patient's CRF. For further details, please refer to the SOPH-A-PORT Mini S IFU.

Patients will have the IDDD removed when they discontinue from the study, unless the patient is continuing to receive treatment through another mechanism (eg, extension study, expanded access program).

7.6 Investigational Product Administration

It is planned that idursulfase-IT will be administered every 28 days by means of the IDDD (or lumbar puncture; See Section 4.1.1). A visual examination of both the port and catheter track will be performed before each IT injection.

A 22-gauge Huber non-coring needle is to be used for access to the implanted port; standard hypodermic needles would damage the septum and may cause leakage. If no needle free connector is present, either a stopcock of the Huber needle infusion set's clamp is to be used to prevent CSF backflow and to mitigate the risk of air entering the system. It is possible to use other brands of Huber non-coring needles, provided that their specifications are identical to that of the Huber needle (22G) supplied by Sophysa in a SOPH-A-PORT Mini S.

If the intrathecal space is not accessible via the IDDD, idursulfase-IT may be administered by lumbar puncture (See Section 4.1.1).

The injection date, injection start/stop time, planned dose, injection volume, and flush volume will be recorded on the patient's CRF.

Intrathecal administration of investigational product will be preceded by CSF sampling for laboratory analysis, pharmacodynamic analysis (GAG concentration), and analyses of idursulfase enzyme concentration and anti-idursulfase antibodies. The total volume of investigational product and flush administered is targeted towards replenishing the volume of CSF withdrawn. Therefore, while the total volume of idursulfase-IT administered will be less than the total volume of CSF withdrawn, additional saline will be administered to ensure a balance between the amount administered and the amount withdrawn.

Specifically, the investigational product will be administered in a volume of 1 mL (1 mL of a 10 mg/mL solution) (See Section 6.1.1). The minimal proposed flush volume is 2 mL, so the minimal volume administered will be 3 mL. Additional volume of preservative-free saline will be administered to add up to a total volume that is equal to that which was withdrawn.

This design was intended to mitigate any risk of overfilling or underfilling the IT compartment as well as the risk of inducing acute intracranial hypertension or brain herniation.

Patients will remain under the observation of study personnel in the hospital setting (eg, may include infusion center, PACU (recovery suite), observation unit, short stay center) for 4 hours post administration of investigational product for safety assessments. Thereafter, if deemed clinically stable by the Investigator, patients may leave the hospital setting (with exception of study visit weeks at which serial blood sampling for pharmacokinetic evaluation is planned). For the first 6 months of treatment with idursulfase-IT, patients must return to the clinic the day after each IT administration for a safety follow-up visit. Note that, under these circumstances, there is no requirement for an overnight hospital stay; if a decision is made to keep the patient overnight for convenience, this hospitalization should not initiate a serious adverse event report. For the latter 6 months of treatment with idursulfase-IT (ie, from Week 28 onward) and in the absence of any safety concerns, patients may complete the safety follow-up visit on the same day as IT administration prior to discharge.

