LIST OF APPENDICES

Appendix 1	Schedule of Events for Patients Randomized to Treatment in the Pivotal Study	97
Appendix 2	Schedule of Events for Patients Randomized to No Treatment in the Pivotal Study	100
Appendix 3	Schedule of Events for Patients Enrolled in the Substudy	102

Appendix 4	Maximum Blood Volume Collection by Study Visit.....	105
Appendix 5	Expected Adverse Device Effects	108
Appendix 6	Protocol Amendment Summary of Changes	110
Appendix 7	Protocol Signature Page	111

SYNOPSIS

Sponsor:

Shire Human Genetic Therapies, Inc.

Names of Investigational Product and Device:

idursulfase for intrathecal use (idursulfase-IT [HGT-2310])

SOPH-A-PORT[®] Mini S, Implantable Access Port, Spinal, Mini Unattached, with Guidewire (SOPH-A-PORT Mini S)

Study Title:

A Controlled, Randomized, Two-arm, Open-label, Assessor-blinded, Multicenter Study of Intrathecal Idursulfase-IT Administered in Conjunction with Elaprase[®] in Pediatric Patients with Hunter Syndrome and Early Cognitive Impairment

Study Number:

HGT-HIT-094

Study Phase:

Phase II/III

Investigational Product Dose, Mode of Administration:

Investigational Product Dose:

Pivotal study - idursulfase-IT 10 mg

Substudy - Dose adjustment for patients below 3 years of age based on reference brain weight: up to 8 months of age at dosing, idursulfase-IT 5 mg; >8 months to 30 months of age at dosing, idursulfase-IT 7.5 mg; >30 months to 3 years of age at dosing, idursulfase-IT 10 mg

Mode of Administration:

intrathecal (IT) injection

Device, Intended Use:

The SOPH-A-PORT[®] Mini S is a system intended for implantation by physicians. The SOPH-A-PORT Mini S, once implanted, allows healthcare personnel to administer idursulfase-IT (HGT-2310) indicated for IT delivery intermittently over a long period of time.

Comparator, Dose, and Mode of Administration:

No treatment

Treatment Regimen:

Once monthly (ie, every 28 days) IT administration of idursulfase-IT for 12 months via a surgically implanted intrathecal drug delivery device (IDDD), or lumbar puncture

Primary Objective:

- To determine the effect of the treatment regimen in pediatric patients with Hunter syndrome and early cognitive impairment on the General Conceptual Ability (GCA) score as measured by the DAS-II, in conjunction with Elaprase therapy

Key Secondary Objective:

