6 STUDY TREATMENT

6.1 Description of Treatments

6.1.1 Investigational Product

The investigational product to be used in this study is idursulfase-IT for intrathecal use.

The idursulfase-IT drug product is an isotonic, sterile solution intended for IT administration. It is formulated as a 10 mg/mL protein concentration in 154 mM NaCl, pH 6.0, 0.005% polysorbate 20. It does not contain any preservatives and is intended for single use.

The active ingredient of the idursulfase-IT drug product is idursulfase (recombinant human iduronate-2-sulfatase) the same active ingredient in the commercially available drug Elaprase. However, Elaprase and idursulfase-IT are specifically formulated for the IV and IT compartments respectively; they cannot be interchanged.

In contrast to Elaprase, idursulfase-IT is specially formulated for, and compatible with, direct introduction into the IT space, because it is isotonic and contains excipients suitable for IT administration.

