6.3 Selection and Timing of Dose for Each Patient

The dosing schedule for the study is described above in Section 6.2.

It is planned that patients randomized to treatment in the pivotal study will undergo surgical implantation of the IDDD. Treated patients will then receive 12 monthly IT injections of idursulfase-IT 10 mg, once every 28 days.

It is planned that patients who are enrolled in the separate substudy will undergo surgical implantation of the IDDD. Patients in the substudy will receive 12 monthly IT injections of idursulfase-IT, once every 28 days. The IT dose of idursulfase-IT to be administered to patients below 3 years of age will be adjusted as follows based on reference brain weight.²⁰

- Up to 8 months of age at dosing, idursulfase-IT 5 mg
- >8 months to 30 months of age at dosing, idursulfase-IT 7.5 mg
- >30 months to 3 years of age at dosing, idursulfase-IT 10 mg

Please refer to the Pharmacy Manual for complete details.

For treated patients in the pivotal study and patients in the substudy, on IT Dosing Weeks, the IV infusion of Elaprase should be scheduled to occur a minimum of 48 hours after IT administration of idursulfase-IT.

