6.9.1 Investigational Product

Idursulfase-IT drug product is a sterile liquid formulation for IT administration that is packaged in 2-mL type-I borosilicate glass vials. The drug product is filled to deliver a minimum dose volume of 1 mL per vial with minimal waste and for handling convenience in the clinical setting.

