7.5 Device Related Procedures

7.5.1 IDDD Implantation and Revision

The IDDD will be surgically implanted or revised at the clinical site. Procedures for implantation and revision are detailed in the device's IFU. Standard hospital procedures for surgery will be followed; the patient will be under general anesthesia for this procedure.

The IFU states the device is contraindicated if the patient's body size is too small to support the size of the SOPH-A-PORT Mini S access port (See Exclusion Criterion 13b). An advisory board consisting of neurosurgeons and medical geneticists convened in October 2014, reached a consensus, and determined the device could be implanted in patients >6 months of age. The corresponding minimum weight and length for a 6-month old boy would be 7.1 kg and 65.4 cm, respectively (15th percentile) according to the World Health Organization (WHO) Child Growth Standards; Weight-for-age Boys: Birth to 5 Years and Length-for-age Boys: Birth to 2 Years.²¹

An additional medical device, the catheter passer, is necessary for the implantation procedure. The catheter passer is a sterile, single use device that will be used in the subcutaneous placement of the catheter. The Phoenix Neuro Disposable Catheter Passer, manufactured by Sophysa is CE marked in the EU and cleared under K853370 in the US and may be provided; however, use of other catheter passers compatible with the SOPH-A-PORT Mini S is allowed.

Details of the implantation/revision and malfunctions/failure will be documented on the patient's CRF.

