8.3.1.4 Post-op Recovery

Surgical implantation of the IDDD will be followed by a post-operative recovery period of at least 14 days prior to the first IT administration of idursulfase-IT.

8.3.2 Patients in the IT Treatment Group of the Pivotal Study and All Patients in the Substudy: IT Dosing (Weeks 4, 8, 12, 16, 20, 24, 28, 32, 36, 40, 44, 48 [\pm 7 days])

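### Protocol 7.6 fixes the injection at 1 mL of 10 mg/mL (10 mg) for everyone, which contradicts the 5 mg and 7.5 mg doses set for substudy patients aged 30 months or less

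*Protocol*

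**What the plan says.** Protocol 7.6 is the general section on giving the product and names no study part. It states that "the investigational product will be administered in a volume of 1 mL (1 mL of a 10 mg/mL solution", pointing for this only to 6.1.1. It adds a flush of at least 2 mL, derives a minimum administered volume of 3 mL, and tops up with saline to equal the CSF withdrawn.

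The substudy doses are set elsewhere. Protocol 6.3 lists "Up to 8 months of age at dosing, idursulfase-IT 5 mg" and ">8 months to 30 months of age at dosing, idursulfase-IT 7.5 mg", with 10 mg above 30 months and up to 3 years. It explains that the adjustment follows reference brain weight and sends the reader to the Pharmacy Manual. The synopsis and SAP 4.1 give the same bands.

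On the product itself, 6.1.1 says "It is formulated as a 10 mg/mL protein concentration in 154 mM NaCl", with no other strength and no dilution step. Section 6.9.1 says "The drug product is filled to deliver a minimum dose volume of 1 mL per vial". The dosing visits are described jointly for both groups in 8.3.2, headed "Patients in the IT Treatment Group of the Pivotal Study and All Patients in the Substudy: IT Dosing", and that section lists the injection without a volume.

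**The concern.** Section 7.6 is where site staff would look for how to give the injection, and its instruction does not match the dose rule for the youngest children. It cannot be read as pivotal-only, because it carries no such limit and substudy dosing visits share the pivotal arm's schedule. Dilution does not reconcile the two, because the sentence fixes concentration as well as volume. The vial does not prevent the error either, since it delivers at least 1 mL.

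At stake is intrathecal dosing in children aged 30 months or less, for whom the dose was deliberately reduced. Protocol 7.16 counts any dose above the mandated one as an overdose, reportable on the SAE form within 24 hours, and notes that no clinical information on overdose exists. As written, one section instructs what another would class as reportable.

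**Working it through.** **Inputs.** Concentration 10 mg/mL (6.1.1, 7.6); product volume 1 mL, minimum flush 2 mL and minimum total 3 mL (7.6); doses 5, 7.5 and 10 mg by age (6.3); device implantable after 6 months of age (7.5.1); at least 14 days of recovery before the first dose (6.2); 12 doses 28 days apart (6.3), visit window ±7 days (8.3.2). I take one month as 30.44 days.

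**The plan's own figures.** Dose = volume × concentration = 1 × 10 = 10 mg. Minimum total = 1 + 2 = 3 mL. Both reproduce, for the 10 mg dose only.

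**Each dose band.** Volume = dose / 10; ratio = 10 / dose; saline for a 3 mL total = 3 − volume.

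| Age at dosing | Assigned dose | Volume needed | Total with 2 mL flush | Saline for 3 mL total | Dose from 7.6 / assigned dose |
|---|---|---|---|---|---|
| Up to 8 months | 5 mg | 0.5 mL | 2.5 mL | 2.5 mL | 2.0 (+5 mg) |
| >8 to 30 months | 7.5 mg | 0.75 mL | 2.75 mL | 2.25 mL | 1.33 (+2.5 mg) |
| >30 months to 3 years | 10 mg | 1 mL | 3 mL | 2 mL | 1.0 |

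The 3 mL minimum does not follow from a 2 mL flush in the two lower bands. It is still reachable, because 2 mL is only the least flush.

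**How many doses could fall in the 5 mg band.** Assume implantation at 6 months, the earliest age consistent with 7.5.1.
- First dose: 6 × 30.44 + 14 = 196.6 days of age.
- End of band: 8 × 30.44 = 243.5 days.
- Doses at 196.6 and 224.6 days fall inside; the next, at 252.6 days, does not. That is 2 of 12.
- If visit windows shorten the spacing to 21 days, doses fall at 196.6, 217.6 and 238.6 days, which is 3 of 12.

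**How many doses could fall in the 7.5 mg band.** Twelve doses span 11 × 28 = 308 days, or 308 / 30.44 = 10.1 months. The band is 30 − 8 = 22 months wide, so all 12 can fall inside it. The planned total is 12 × 7.5 = 90 mg; a literal reading of 7.6 gives 12 × 10 = 120 mg.

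**The case against.** The strongest reply is that 6.3 is the dose-selection section and governs over a general administration paragraph. It states the bands explicitly and cites the Pharmacy Manual, which may well give 0.5 mL and 0.75 mL. The disputed sentence is mainly about balancing fluid volumes, and saline makes up the total at any product volume. Section 6.10.1 says to withdraw the product without fixing a volume and again cites the manual. Staff are to be trained and to know the patient's regimen (6.8), and planned dose and injection volume are both recorded on the CRF, so a mismatch would show.

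The 5 mg band is also very thin. Criterion 4 in 5.2.2 requires 4 months of Elaprase immediately before Screening. With implantation at 6 months and 14 days after Day 0, and 1 to 28 days of screening, Elaprase must have started at 182.6 − 14 − (1 to 28) − 121.8, or about 19 to 46 days of age. Section 4.2 calls measurable impairment before 3 years rare. Section 4.2.1 reports equivalent safety profiles for 1, 10 and 30 mg in Phase I/II.

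Most of this stands as a limit on likelihood. It is right that the absence of the lower volumes from the available documents does not prove that sites lacked them, and that the 120 mg total needs the same error at every dose. It does not correct 7.6: an open instruction in 6.10.1 does not override a specific figure, CRF recording detects an error only after the injection, and the Phase I/II result does not establish safety at these ages. The early Elaprase start makes the 5 mg band rarer without emptying it.

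**Conclusion.** The concern holds. The arithmetic in 7.6 is correct for 10 mg; the fault is an internal inconsistency, because the sentence lacks a limit to that dose. Read literally it doubles the assigned dose up to 8 months of age and raises it by a third from over 8 to 30 months. The first case could touch about 2 of 12 doses (3 with shortened spacing), assuming implantation just after 6 months. The second could touch all 12, with 120 mg against 90 mg as a ceiling and not an expected outcome.

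The volumes of 0.5 mL and 0.75 mL assume that the product is used undiluted at 10 mg/mL. No actual misdosing or wrong PK dose assignment is shown. The pivotal dose, sample size and efficacy analysis are untouched, since the pivotal dose is 10 mg and the substudy is analysed separately. It should still be fixed, because it concerns an intrathecal volume in very young children and the correction is almost free.

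**What to change.** In Protocol 7.6:
- Limit the 1 mL statement to the 10 mg dose.
- Add 0.5 mL for 5 mg and 0.75 mL for 7.5 mg at 10 mg/mL, after confirming both against the Pharmacy Manual.
- State that the saline is adjusted so that the total equals the CSF withdrawn; for a 3 mL total this is 2.5 mL and 2.25 mL respectively.
- Cross-refer to 6.3 and the Pharmacy Manual.

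The cost is one or two sentences, or a clarification letter to sites. Design, analysis and data collection do not change. If the manual already gives the right volumes, the edit only brings the protocol into line with it.

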7.7 Pharmacokinetic Assessments

Blood samples will be collected for determination of idursulfase serum concentration-time profiles and serum pharmacokinetic parameters after IT administration.

Idursulfase concentrations will be measured in CSF samples obtained immediately prior to each IT administration (and at the EOS Visit) to determine the degree of accumulation of monthly idursulfase-IT administrations in the CSF.

The blood and CSF sampling schedules for pharmacokinetic assessments are provided in the SOE for patients in the treated arm of the pivotal study ([Appendix 1](#)) and in the separate substudy ([Appendix 3](#)).

7.8 Pharmacodynamic/Biomarker Assessments

7.8.1 CSF Glycosaminoglycan

Cerebrospinal fluid will be collected for measurement of the concentration of GAG (refer to the SOE for the pivotal study [[Appendix 1](#) and [Appendix 2](#)] and separate substudy [[Appendix 3](#)]).

7.8.2 CSF and Serum Albumin

Albumin levels will be measured in samples of CSF (refer to the SOE for the pivotal study ([Appendix 1](#) and [Appendix 2](#)) and separate substudy ([Appendix 3](#)) to monitor the permeability of the blood-brain barrier. Measurement of albumin levels in serum is included in the panel of clinical laboratory tests ([Table 7-2](#)).

7.9 Efficacy Assessments

The efficacy endpoints are specified in [Section 3](#).

7.9.1 Neurodevelopmental Assessment Tools

The study methodology will include standardized neurodevelopmental assessments to provide a quantifiable measure of patient neurodevelopmental status.⁶ Neurodevelopmental status will be assessed over time by measuring cognitive and adaptive functions as follows.

Cognition: the Differential Ability Scales, Second Edition (DAS-II)¹⁶ will be used to assess all randomized patients. The DAS-II comprises 2 overlapping batteries. The Early Years battery is designed for children ages 2 years 6 months through 6 years 11 months. The School Age Battery is designed for children ages 7 years 0 months through 17 years 11 months. These batteries are fully co-normed for ages 5 years 0 months through 8 years 11 months.

For patients participating in the separate substudy only (ie, patients who are below the age of 3 years and who have early cognitive impairment) cognition will be assessed initially using the Bayley Scales of Infant Development, Third Edition (BSID-III).¹⁹ When these patients reach at

least 42 months of age, if considered evaluable using the DAS-II instrument, they will transition to use of the DAS-II for continued assessment of cognition.

Adaptive Behaviors: the Vineland Adaptive Behavioral Scales, Second Edition (VABS-II)¹⁸ will be used to assess all patients. The Expanded Interview Form will be utilized.

It is intended that full neurodevelopmental assessments be conducted for all patients; however, it is recognized that the feasibility of conducting these assessments may be dependent on the patient's ability to cooperate and/or level of cognitive impairment.

All assessments will be administered by qualified study personnel. The DAS-II will be administered by a trained practitioner.

7.10 Health Status Assessment

The health status of patients will be assessed using the EuroQol-5D (EQ-5D) questionnaire, a standardized instrument for use as a measure of health status which is applicable to a wide range of health conditions and treatments.^{22,23} The EQ-5D provides a descriptive profile and index value for health status.

7.11 Safety Assessments

Safety will be assessed by adverse events (by type, severity, and relationship to treatment [idursulfase-IT, the IDDD, device surgical procedure, or IT administration process] and IV Elaprase infusion), changes in clinical laboratory testing (serum chemistry, hematology, urinalysis), physical and neurological examination, vital signs, 12-lead ECG recordings, CSF laboratory parameters (chemistries, cell counts), anti-idursulfase antibodies in CSF and serum, and determination of antibodies having enzyme neutralizing activity.

SOPH-A-PORT Mini S assessments will include measures of device implantation, device function, device longevity, and adverse events associated with the implant surgery or device. This data will be collected on the patient's CRF from the time of initial implantation.

7.11.1 Physical and Neurological Examination

A physical examination will be performed with a thorough review of body systems on specified study days.

Physical examinations will include a review of the patient's general appearance, neurological examination, as well as evaluation of the body systems listed in [Table 7-1](#) and the device port and catheter track. Any abnormal change in findings will be recorded as an adverse event on the appropriate CRF.

Table 7-1 Assessments for Physical and Neurological Examinations

Assessment	Assessment
General appearance	Endocrine

Table 7-1 Assessments for Physical and Neurological Examinations

Assessment	Assessment
Head and neck	Cardiovascular
Eyes	Abdomen
Ears	Genitourinary
Nose	Skin
Throat	Musculoskeletal
Chest and lungs	Neurological
Port and catheter	

7.11.2 Height and Weight

Height (cm) and weight (kg) will be recorded for all patients at Screening and during the study at time points specified in the SOE. The clinical site staff will be instructed to use a calibrated scale for weight measurement.

7.11.3 Head Circumference

Head circumference (cm) will be measured in a uniform manner for all patients.

7.11.4 Hearing Assessment

Each patient must have sufficient auditory capacity, with a hearing aid(s), if needed, in the Investigator’s judgment, to complete the required protocol testing and must be compliant with wearing the hearing aid(s), if needed, on scheduled testing days.

The Investigator will confirm that, with hearing aids in place if needed, each patient has sufficient understanding to participate in study assessments.

